#### 2.2.3 Multiple imputations for response variables

Non-responder imputation as primary analysis will be performed since low drop-out rates are expected. It is expected that subjects will be likely to drop-out due to lack of efficacy, such that a non-responder imputation will be reasonable.

In the multiple imputations analysis the response status will be imputed based on the individual treatment arm information.

Multiple imputation (MI) is a simulation based approach where missing values are replaced by multiple Bayesian draws from the conditional distribution of missing data given the observed data and covariates, creating multiple completed data sets. These completed data sets can then be analyzed using standard methods. Rubin (1987) presented rules how to combine the multiple sets of estimates to produce overall estimates and confidence intervals that adequately incorporate missing data uncertainty.

Missing values for the 'change from baseline PASI score' will be imputed based on an underlying joint normal distribution and using a Markov Chain Monte Carlo (MCMC) method. The change from baseline in PASI score appears to follow closer to a normal distribution than the actual PASI score.

Page 41

The imputations will be done separately for each dosing group including weight at Week 24 (in groups) as additional covariate. Values post assessment timepoint of the primary endpoint will not be considered for imputations.

The number of imputations will be set to 50, the seed for the random function will be set to 4573302 for this study. To generate the multiple imputed data sets, the SAS procedure MI can be used as follows:

The input data set <pasi> should have one record per subject with baseline PASI score as well as all changes from baseline PASI starting with Week 28.

```
ODS LISTING CLOSE;
ODS OUTPUT MissPattern=miinfo_msgpat VarianceInfo=varinfo ParameterEstimates=param;
PROC MI DATA=<pasi> OUT=<impdata> SEED=4573302 NIMPUTE=50;
 VAR <weight at Week 24> >
     <baseline PASI>
     <change from baseline PASI week 24> - <change from baseline PASI week primary endpoint>;
RUN;
ODS LISTING;
```

Two outputs will be prepared displaying i) the missing data patterns and the group means as stored in the data set msgpat and ii) the variance information and estimated means with confidence interval and range based on data sets varinfo and param which need to be merged by <dosing group>.

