#### Programming notes:

- The SAS procedure MIANALYZE expects a variable called " IMPUTATION which is generated by the MI procedure. It might be needed to set the SAS option "VALIDVARNAME=UPCASE" temporarily in the program before the MI call, this option should be reset after the MIANALYZE call to VALIDVARNAME=V6.
- In case there are no missings in one dosing group, the MI procedure does not impute any values. In this case the corresponding data need to be imputed manually outside PROC MI and added to the dataset <impdata>.

The imputed data are saved in data set <impdata>. The outcome of interest, i.e. the PASI 90 response will be calculated as follows:

```
DATA <impdata2>;
SET <impdata>;
IF <change from baseline PASI week primary endpoint>/<baseline PASI> >=0.90 THEN <PASI 90
response> =1;
ELSE <PASI 90 response>=0;
RUN;
```

The treatment differences for each imputed data set will then be evaluated by means of logistic regression models as described in Section 2.2.2. This analysis will be done by **Novartis** 

IMPUTATION for the comparison to the control group. A data set containing the estimated parameters of the logistic regression will be created (ods output ParameterEstimes=Igsparms).

The estimates based on the 50 imputed data are then combined by applying Rubin's rules for multiple imputed data sets, see Little and Rubin (2002). For this estimation the SAS procedure MIANALYZE will be used (parms=Igsparms, modeleffects <Treatment group>). ODS OUTPUT data sets containing ParameterEstimates, VarianceInfo and ModelInfo will be produced.

The data set ParameterEstimates contains the estimate for the log(odds ratio) and the lower and upper confidence intervals. These three variables will be back-transformed and presented in the results.

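### The multiple-imputation check draws PASI change from an unbounded normal model, which under-imputes PASI 90 response; its template code also lacks the by-dosing-group split the text requires

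*SAP*

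**What the plan says.** The primary analysis counts a patient without a valid Week 52 PASI as a non-responder (SAP 1.8.3). SAP 1.8.4 lists three supportive analyses: (A) a risk difference, (B) a per-protocol repeat and (C) multiple imputation, with details in 2.2.3.

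Under 2.2.3, missing change from baseline in PASI "will be imputed based on an underlying joint normal distribution and using a Markov Chain Monte Carlo (MCMC) method". The reason given is: "The change from baseline in PASI score appears to follow closer to a normal distribution than the actual PASI score". On the arms, the text states: "The imputations will be done separately for each dosing group including weight at Week 24 (in groups) as additional covariate".

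The code is introduced with "the SAS procedure MI can be used as follows", and the call is "PROC MI DATA=<pasi> OUT=<impdata> SEED=4573302 NIMPUTE=50". Its variable list holds weight at Week 24, baseline PASI and the changes from Week 24 to the primary time point. As printed it has no BY statement, no dosing-group variable and no bound on the imputed values. The resulting variance and parameter data sets "need to be merged by <dosing group>". Response is then set by "IF <change from baseline PASI week primary endpoint>/<baseline PASI> >=0.90 THEN <PASI 90" and so on.

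**The concern.** Everyone in the FAS-P90R had a Week 24 PASI at or below 10% of baseline, and PASI is bounded at 0. Values should therefore sit at or near 0 with a long right tail. A normal model takes its spread from that tail, places part of its mass below 0, and places too much above the 10%-of-baseline cut. Response is then under-imputed. Analysis (C) is the only supportive analysis that models the missing outcomes, so a reader would take it as the missing-at-random counterpart to non-responder imputation.

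The second issue is that text and code disagree on whether the arms are imputed separately. A shared model pulls the arms together, which is the favourable direction in a non-inferiority trial.

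**Working it through.** **1. Plan figures used for calibration.** From SAP 1.11: 81.8% and 74.8% maintenance, margin 15 points, one-sided 2.5%, 90% power.

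n = (1.960 + 1.282)² × (0.818×0.182 + 0.748×0.252) / (0.15 − 0.07)² = 10.507 × 0.3374 / 0.0064 = 554 per group, as stated.

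Odds-ratio margin: (0.818/0.182)/(0.668/0.332) = 2.234, stated as 2.23. Section 2.2.3 itself gives no figure on imputation accuracy.

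**2. Does using change help?** Write B for baseline and P for a later score, with change C = B − P. The set (B, B − P24, …, B − P52) is an invertible linear transformation of (B, P24, …, P52). A joint normal model for one set is a joint normal model for the other. Given B, C is P reversed and shifted by a constant: same spread, mirrored skew, and the floor P ≥ 0 becomes the ceiling C ≤ B. Change may look more normal marginally because baseline varies between patients, but the model conditions on baseline.

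**3. Hand check of the mechanism.** The inputs are assumed, because the documents give none: mean baseline about 21, so the cut is about 2.1; Week 52 PASI mean 1.28, SD 2.00, from a skewed distribution set to 81.8% response.

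- Normal response rate: Φ((2.1 − 1.28)/2.00) = Φ(0.41) = 66%, against a true 81.8%.
- Share of draws below 0: Φ(−1.28/2.00) = Φ(−0.64) = 26%.

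**4. Simulation.** Assumptions: log-normal residual PASI with 30 to 50% of patients clear at Week 24; maintenance 81.8% and 74.8%; monotone dropout completely at random; Bayesian normal regressions on weight group, baseline and earlier changes, which for monotone data are equivalent to the joint normal draw. Results at 10% missing, in per cent (differences in points; the true difference is 7.00):

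| Serial correlation / log SD / clear | Missing, 4-weekly: true → imputed | Missing, 6-weekly: true → imputed | Overall imputed, 4- / 6-weekly | Difference, by arm | Difference, pooled |
|---|---|---|---|---|---|
| 0.3 / 1.0 / 30% | 81.7 → 66.9 | 74.4 → 57.3 | 80.3 / 73.1 | 7.27 | 6.59 |
| 0.5 / 1.2 / 40% | 81.0 → 65.0 | 74.2 → 56.1 | 80.2 / 73.0 | 7.22 | 6.62 |
| 0.7 / 1.2 / 40% | 82.7 → 67.0 | 74.5 → 58.2 | 80.2 / 73.2 | 7.01 | 6.34 |
| 0.3 / 1.6 / 40% | 82.1 → 55.7 | 74.7 → 49.9 | 79.3 / 72.3 | 6.94 | 6.54 |
| 0.7 / 1.6 / 50% | 81.9 → 61.7 | 75.0 → 54.1 | 79.8 / 72.7 | 7.14 | 6.53 |
| 0.5 / 0.8 / 30% | 82.5 → 71.5 | 74.3 → 61.7 | 80.7 / 73.6 | 7.15 | 6.43 |

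The shortfall among missing patients is 11 to 26 points, and the same at 5% missing. By arm, between 18 and 34% of imputed PASI values are negative.

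**5. Effect on the comparison.** The fall in an arm's overall rate is the missing fraction times the shortfall: from 0.05 × 11 = 0.6 to 0.10 × 26 = 2.6 points. Both arms fall by similar amounts, so the by-arm difference stays within 6.9 to 7.3 at 5 or 10% missing; other skewed set-ups move it by up to about 0.4. On the odds-ratio scale the truth is (81.8/18.2)/(74.8/25.2) = 1.51. The fourth row gives (79.3/20.7)/(72.3/27.7) = 1.47 and the first gives (80.3/19.7)/(73.1/26.9) = 1.50. The limit is 2.23.

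**6. Code against text.** Without a BY statement the output data sets carry no dosing-group variable to merge on, so the listing does not support the step that follows it. Run pooled, the difference is smaller than by arm by 0.4 (6.94 − 6.54) to 0.7 points (7.15 − 6.43) at 10% missing and by 0.2 to 0.4 at 5%. Across all set-ups tried the range is about 0.1 to 0.9.

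**7. Two loose ends in the same section.** The input data set is described as holding changes from Week 28, but the variable list starts at Week 24. The 0.90 rule needs change as baseline minus later value, while the SAP's explicit change formulas (1.9.2, 1.9.3) are later value minus baseline.

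**The case against.** Several points on the other side stand.

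- **Small effect.** Only patients with missing Week 52 PASI are imputed, and the SAP expects few dropouts. In a separate skewed set-up with random dropout, the approximate unadjusted upper limit of the odds ratio moved by 0.03 to 0.08 and stayed below 2.23.
- **By-arm imputation is clearly intended.** The text says so, the outputs are merged by dosing group, and the programming notes cover an arm with no missing values. The code is a template, and a stray symbol in its variable list shows that the listing is damaged, so a line lost in PDF reading cannot be excluded.
- **Dropout may not be random.** The SAP expects dropout for lack of efficacy. With dropout made likelier after loss of PASI 90, the true rate among missing patients was about 69 to 71% and 62 to 63%, and the shortfall narrowed to roughly 13 to 22 points. It did not disappear.

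A reader might also infer more than the documents support.

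- **A fixed misclassified share, such as a fifth of responders.** The share is 1 − Φ((0.1B − m)/s) for assumed mean m and SD s. Over B 15 to 25, m 0.5 to 1.5 and s 0.5 to 3 it runs from 0 to 50%. A share near a fifth would not in itself show bias: a calibrated draw without predictors would call 18.2% and 25.2% of true responders non-responders. The imputed rate among missing patients is the proper measure.
- **That (C) merely reproduces non-responder imputation.** At 10% missing, non-responder imputation gives 0.90 × 81.8 = 73.6% in the 4-weekly arm. The normal model gives 79.3 to 80.7%, against a true 81.8%, so (C) remains a distinct check.
- **That no other analysis bears on missing data.** Analysis (B) is limited to patients who finish as planned and is in effect a completer analysis, although it also removes major deviators.

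**Conclusion.** The concern holds as a flaw in a sensitivity analysis. The normal draw does not suit a bounded, skewed score, and the reason given for using change does not repair it because baseline is in the model. That part needs no assumption beyond skewed PASI in Week 24 responders. The size does rest on assumptions: with the skewed distributions tried and random dropout, response among missing patients is under-imputed by about 11 to 26 points in both arms. At 5 to 10% missing this costs about 0.6 to 2.6 points per arm and about 0 to 0.4 points on the by-arm difference. The non-inferiority decision is unlikely to change, and the primary analysis is untouched. What is lost is an unbiased missing-at-random check.

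The missing BY statement is a secondary conflict between text and template. A reader might infer that the arms will be pooled to the benefit of non-inferiority. The text says the opposite, and even pooled as printed the shrinkage relative to by-arm imputation is about 0.1 to 0.9 points.

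**What to change.** In SAP 2.2.3:

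- Replace the joint normal MCMC draw with predictive mean matching for the PASI score (FCS or MONOTONE REGPMM), which takes values from observed donors and so cannot go below 0. Alternatively, impute Week 52 PASI 90 status directly by logistic regression. In simulation, matching by dosing group came within about 3 points of the true rate among missing patients, and logistic imputation gave 81 to 82% and 74 to 75% against about 82% and 75%. The logistic route discards the continuous PASI path and may be less stable with few missing patients per arm.
- Add BY dosing group to the PROC MI code.
- State one starting week for the input data set and the variable list.
- Define change in PASI as baseline minus later value, so that the 0.90 rule works.

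The cost is a short SAP revision, slightly more programming and a convergence check. The sample size and the primary analysis do not change.

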#### Programming notes:

- The SAS procedure MIANALYZE expects a variable called " IMPUTATION which is generated by the MI procedure. It might be needed to set the SAS option "VALIDVARNAME=UPCASE" temporarily in the program before the MI call, this option should be reset after the MIANALYZE call to VALIDVARNAME=V6.
- In case there are no missings in one dosing group, the MI procedure does not impute any values. In this case the corresponding data need to be imputed manually outside PROC MI and added to the dataset <impdata>.

The imputed data are saved in data set <impdata>. The outcome of interest, i.e. the PASI 90 response will be calculated as follows:

```
DATA <impdata2>;
SET <impdata>;
IF <change from baseline PASI week primary endpoint>/<baseline PASI> >=0.90 THEN <PASI 90
response> =1;
ELSE <PASI 90 response>=0;
RUN;
```

The treatment differences for each imputed data set will then be evaluated by means of logistic regression models as described in Section 2.2.2. This analysis will be done by **Novartis** 

IMPUTATION for the comparison to the control group. A data set containing the estimated parameters of the logistic regression will be created (ods output ParameterEstimes=Igsparms).

The estimates based on the 50 imputed data are then combined by applying Rubin's rules for multiple imputed data sets, see Little and Rubin (2002). For this estimation the SAS procedure MIANALYZE will be used (parms=Igsparms, modeleffects <Treatment group>). ODS OUTPUT data sets containing ParameterEstimates, VarianceInfo and ModelInfo will be produced.

The data set ParameterEstimates contains the estimate for the log(odds ratio) and the lower and upper confidence intervals. These three variables will be back-transformed and presented in the results.

#### Crude incidence and 100\*(1-α)% confidence interval 2.2.4

For n subjects, each at risk to experience a certain event with probability  $\pi$ , the crude incidence is estimated as p=x/n, where x is the number of subjects with the event.

Absolute and relative frequencies will be displayed as well as 95% confidence interval for the relative frequency based on the score method including continuity correction (Newcombe 1998).

#### 2.3 Analysis of time-to-event data

Number and percentage of subjects with a clinical event based on the number of subjects in the analysis set at risk as denominator will be provided by treatment group.

For each time-to-event variable, between-treatment differences will be evaluated using a logrank test, stratified by country and weight at Week 24 (<90 kg or ≥90 kg) to compare the survival functions between the dosing groups. The hazard ratios for these comparisons for the variable and their corresponding 95% confidence intervals will be computed using a stratified, Cox proportional hazards regression model with dosing group and baseline PASI as explanatory variable and stratified by country and weight at Week 24. The SAS procedure PHREG, with option STRATA if applicable, will be used to perform the analysis. The Kaplan-Meier estimates of the survival functions for each treatment will be plotted. The plot will include the number of subjects at risk for each treatment group at pre-specified timepoints (e.g., visits). Median time to event and quartiles including 95% confidence intervals will be provided. The confidence intervals will be based on log-log transformation. (PROC LIFETEST option conftype=log-log; default in SAS 9.2). In addition, for pre-specified time intervals the following will be presented in an output:

for each treatment group and time interval: subjects at risk, subjects with event, subjects with event divided by subjects at risk, cumulative subjects with event and cumulative event probability including 95% confidence interval

The pre-specified time intervals for Treatment Period 2 are as follows: "\( \leq 4 \) weeks", "\( > 4 \) weeks to  $\leq 8$  weeks", ">8 weeks to  $\leq 12$  weeks", ">12 weeks to  $\leq 16$  weeks", ">16 weeks to ≤20 weeks", ">20 weeks to ≤24 weeks", ">24 weeks to ≤28 weeks" and ">28 weeks".

Subjects at risk, timepoint "0" and censoring will be defined as described in Table 2-1 below.

Table 2-1	i ime to	event: defin	ition of risk se	et, timing an	a censoring i	by variable
Variable: Time to	Risk set	Time = 0	Time of event	Censoring	Psoriasis ConMed	Informative censoring
PASI 90 response	FAS-P75R	Date of randomi- zation (Week 24)	Date of 1 st visit with PASI 90 response observed	End of Treatment Period 2 (Week 52 visit)	Censor (if ConMed taken before the event)	No
Loss of PASI 90 response	FAS-P90R	Date of randomi- zation (Week 24)	Date of 1 st visit with OBSERVED loss of PASI 90 response (i.e. no imputation for missing values)	End of Treatment Period 2 (Week 52 visit)	Event (if the subject took psoriasis ConMed, the subject is considered as having lost response)	Study phase discontinu- ation with reason "lack of efficacy"
Loss of PASI 75 response	FAS-P75R	Date of randomi- zation (Week 24)	Date of 1 st visit with OBSERVED loss of PASI 75 response (i.e. no imputation for missing values)	End of Treatment Period 2 (Week 52 visit)	Event (if the subject took psoriasis ConMed, the subject is considered as having lost response)	Study phase discontinu- ation with reason "lack of efficacy"
Loss of IGA mod 2011 0 or 1 response	- All IGA 0 or 1 responders at Week 24 in FAS- P90R - All IGA 0 or 1 responders at Week 24 in FAS- P75R	Date of randomi- zation (Week 24)	Date of 1 st visit with OBSERVED loss of IGA mod 2011 0 or 1 response (i.e. no imputation for missing values)	End of Treatment Period 2 (Week 52 visit)	Event (if the subject took psoriasis ConMed, the subject is considered as having lost response)	Study phase discontinu- ation with reason "lack of efficacy"

ConMed: Concomitant medication

Psoriasis ConMed is defined in MAP appendix

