#### 1.4.3 Screening, baseline and post-baseline definitions

Screening refers to any procedures (e.g., checking inclusion and exclusion criteria) performed prior to the date of visit 2. Per protocol, subject informed consent must be obtained prior to performing any study related activity. The date of signing informed consent is the start date of screening period. Any assessment obtained during the screening period will be labeled screening assessment.

Visit 2 is defined as *Baseline* visit. All consecutive visits are labeled according to the preplanned study week where they occur, i.e. Week 1, Week 2, and so on.

Week 24 is defined as the end of Treatment Period 1 (visit 11) for patients without premature discontinuation during Treatment Period 1. For patients with premature termination within Treatment Period 1 the last visit is defined as end of Treatment Period 1.

Week 52 is defined as the end of Treatment Period 2 (visit 18) for patients without premature discontinuation during Treatment Period 2. For patients with premature termination in Treatment Period 2 the last visit is defined as end of Treatment Period 2.

Any visits and assessments occurring after the end of Treatment Period 2 visit (Week 52 in the eCRF) will be aligned to the Week 60 Follow-Up visit.

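### Time to PASI 90 in Groups 3 and 4 censors likely treatment failures as uninformative, so the Kaplan-Meier response curves run too high, by an amount that is probably small

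*SAP*

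**What the plan says.** SAP Table 2-1 (section 2.3) sets the rules for four time-to-event variables. For time to PASI 90 response in FAS-P75R (Groups 3 and 4), the psoriasis-medication rule is "Censor (if ConMed taken before the event", and the entry in the column headed "Informative censoring" is No. All other censoring is at the end of Treatment Period 2. SAP 1.4.3 fixes that date for early leavers: "For patients with premature termination in Treatment Period 2 the last visit is defined as end of Treatment Period 2".

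The three loss-of-response rows differ. Psoriasis medication is an event there ("if the subject took psoriasis ConMed, the subject is considered as having lost response"), and discontinuation for lack of efficacy is entered as informative. One of these rows, loss of PASI 75, uses the same FAS-P75R patients.

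Two other places bear on the point. SAP 2.2.3 justifies non-responder imputation by saying "It is expected that subjects will be likely to drop-out due to lack of efficacy". SAP 1.8.3 counts early drop-outs as non-responders for the key secondary endpoint, also in FAS-P75R.

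**The concern.** Reading one minus Kaplan-Meier as the probability of reaching PASI 90 requires that censored patients would have responded at the rate of those still followed. For patients who leave because the drug is not working, or who turn to other psoriasis treatment before responding, the plan's own statements point the other way. Removing them shrinks the denominator at later visits but not the numerator, so the curve rises too far. The cumulative event probabilities, their confidence intervals, and any median or quartile that is reached all carry the bias.

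Time to clear or almost clear skin, 2-weekly against 4-weekly, is a stated exploratory objective (Protocol 2.3, SAP 1.1), so these curves are likely to be shown. The same patient starting the same medication on the same day is a failure in the loss-of-PASI-75 curve and uninformatively censored in the PASI 90 curve.

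**Working it through.** **The plan's own figure.** The documents give none for this analysis. The nearest is the key secondary power in Protocol 9.7.1: 1580 × 13.3% = 210 patients, 105 per group, about 4% v 18% at Week 52, two-sided 5%, more than 90% power. With pooled variance under the null:

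z = [0.14 − 1.96 √(2 × 0.11 × 0.89 / 105)] / √[(0.04 × 0.96 + 0.18 × 0.82) / 105] = (0.1400 − 0.0846) / 0.0421 = 1.32, so power is 90.6%. It reproduces.

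**Hand check of the bias.** Take 105 per arm. Assume that half of the responders respond before mid-period, that failures (leaving for lack of efficacy, or psoriasis medication before response) occur at mid-period in 10% (4-weekly) and 4% (2-weekly), and that failures never respond. Censoring the failures gives:

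- Response 4% v 18%
  - 4-weekly: 1 − (1 − 2.1/105)(1 − 2.1/92.4) = 4.23%, inflation 0.23 points
  - 2-weekly: 1 − (1 − 9.45/105)(1 − 9.45/91.35) = 18.41%, inflation 0.41 points
  - difference: 14.2 instead of 14.0 points (wider)
- Response 40% v 55% (assumed any-visit rates)
  - 4-weekly: 1 − (1 − 21/105)(1 − 21/73.5) = 42.9%, inflation 2.9 points
  - 2-weekly: 1 − (1 − 28.875/105)(1 − 28.875/71.925) = 56.6%, inflation 1.6 points
  - difference: 13.7 instead of 15.0 points (narrower)

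**Seven-visit model.** There are seven four-weekly visits after Week 24. Let R be the response probability that Kaplan-Meier shows at Week 52 and F the 28-week failure probability with response set aside, both with constant hazards: h = 1 − (1 − R)^(1/7) and m = 1 − (1 − F)^(1/7). With failure taken before response at each visit, the share who actually reach PASI 90 is

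CIF = h(1 − m)[1 − (1 − R)(1 − F)] / [1 − (1 − m)(1 − h)].

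Example with R = 25%, F = 20%: h = 0.0403, m = 0.0314, CIF = 0.0403 × 0.9686 × 0.40 / 0.0704 = 22.17%, against 25% on the curve.

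All F are assumptions, and so are all R except 4% v 18%. Entries are 4-weekly / 2-weekly, in percent or points; differences were taken before rounding.

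| R | F | CIF | Inflation | Relative inflation | Difference: KM, CIF |
|---|---|---|---|---|---|
| 4 / 18 | 2 / 2 | 3.95 / 17.80 | 0.05 / 0.20 | 1.2% / 1.1% | 14.00, 13.85 |
| 4 / 18 | 10 / 5 | 3.77 / 17.50 | 0.23 / 0.50 | 6.1% / 2.9% | 14.00, 13.73 |
| 4 / 18 | 20 / 10 | 3.53 / 16.98 | 0.47 / 1.02 | 13.3% / 6.0% | 14.00, 13.45 |
| 4 / 18 | 30 / 5 | 3.28 / 17.50 | 0.72 / 0.50 | 21.8% / 2.9% | 14.00, 14.21 |
| 25 / 45 | 20 / 5 | 22.17 / 43.81 | 2.83 / 1.19 | 12.8% / 2.7% | 20.00, 21.65 |
| 40 / 55 | 30 / 5 | 33.28 / 53.59 | 6.72 / 1.41 | 20.2% / 2.6% | 15.00, 20.31 |

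The curve is too high in every row. Relative inflation is larger in the arm with more failures. Absolute inflation is larger in the 4-weekly arm only above a break-even ratio of failure rates (4-weekly over 2-weekly): about 4.3 at 4% v 18%, 2.9 at 10% v 30%, and 1.7 at 25% v 45%.

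**The case against.** - **The rows need not match.** Failure can be the event in a loss-of-response analysis but not in a time-to-response analysis, where the choice is between censoring and a competing-risk method. Censoring at psoriasis medication also avoids crediting secukinumab with a response helped by another drug. This stands as a reason for the present rule, but the fix below credits no such response either.
- **The Cox model is not invalid.** Its estimate can be read as a cause-specific hazard ratio, which does not require censored patients to resemble the rest. This stands. It does not rescue the Kaplan-Meier probabilities.
- **Exposure is probably small.** Rescue medication is not permitted (Protocol 5.5.6), psoriasis treatment is largely limited to bland emollients (Protocol 5.5.7.2), and non-responder imputation is chosen "since low drop-out rates are expected" (SAP 2.2.3). This stands as to size. However, Protocol 5.5.8 lets a patient who has used a prohibited treatment stay in the study after stopping it, so cases can arise. What counts as psoriasis medication is defined in an appendix outside these documents.
- **The crude proportion is also planned.** SAP 2.3 reports the percentage with the event on the full denominator, so a reader could see a gap. It does not correct the curve.
- **Only half of the contrast with the loss rows is written out.** Psoriasis medication is scored there as an event. Discontinuation for lack of efficacy is only labelled informative, and no text says how it is scored. A reader might infer that the SAP scores both as failure; the documents support that for medication alone.

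**Conclusion.** The point holds as a cheap improvement to an exploratory analysis. The Kaplan-Meier probabilities of reaching PASI 90 in Groups 3 and 4 are biased upward if, as the SAP expects, leavers are mainly treatment failures, and the bias is relatively larger in the arm with more of them. At the protocol's 4% v 18% it is roughly 0.05 to 1 point over the failure rates tried (2% to 30%). At 25% v 45% with failures of 20% and 5% it is about 1 to 3 points. It approaches 7 points only at 40% response with 30% failures. These sizes assume that failures never respond and that hazards are constant.

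A reader might infer that the bias is greatest in the weaker arm and shrinks the contrast against 2-weekly dosing. The documents do not show this: they give no failure rates by arm, and at 4% v 18% the absolute bias is usually larger in the 2-weekly arm, with the difference slightly widened.

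A reader might also blame this rule for any disagreement between the curve and the Week 52 analysis. Part of that gap would remain in any case, because the curve counts the first visit with PASI 90 and the key secondary endpoint counts response at Week 52. No confirmatory claim rests on this analysis, which is outside the testing hierarchy in SAP 1.8.6.

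**What to change.** In the PASI 90 response row of Table 2-1, keep patients who discontinue for lack of efficacy, or who take psoriasis medication before response, in the risk set as event-free to the planned Week 52 day (Day 365 in Table 1-3), and do not count any later response after the medication. Reporting cumulative incidence with failure as a competing event targets the same quantity. Censor at last visit only for other reasons. Keep the present rule as a sensitivity analysis, describe its Cox estimate as a cause-specific hazard ratio, and state how the informative-censoring entries in the loss rows are scored.

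The cost is one table row and one derived date. The downside is that the curve becomes a composite that counts treatment failure as no response. That matches the key secondary rule for leavers but not fully for medication users, because SAP 1.8.3 keeps the observed response of patients with major protocol violations who have a valid Week 52 PASI.
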